6 STUDY DESIGN AND PROCEDURES

6.1 Experimental Design and Randomization

We will test our hypotheses using a two arm-randomized control trial. In exploratory analyses, we will examine individual differences in response to treatment. We will collect outcome data at 3 time points: baseline, and 6 (-2 weeks/+4 weeks) and 12 months (-2 weeks/+4 weeks) after initial engagement with CareAvenue. Data collectors and analysts will be blind to the study hypotheses, and analysts will be further blinded by which group participants are allocated to.

Participants will be randomized to either usual care or the intervention group receiving CareAvenue. Usual care is defined as existing practices for addressing patients' financial burden and non-medical issues in the clinic flow. We will provide all control group participants with contact information for the Guest Assistance Program (GAP) at the University of Michigan Health System (UMHS). GAP provides assistance with medical and non-medical needs and resources to patients receiving medical care at UMHS. It consists of social workers who work with clients to help them access a variety of resources. Providing contact information for GAP to the control arm will ensure another layer of blinding of the intervention, and provides an opportunity to assess the benefits of an autonomy supportive, multi-component skills-training intervention on outcomes.

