follow-up (IVR), 2) self-management support (IVR), 3) behavioral reinforcement (text-message), 4) motivation (text-message). These methods have a proven track record for fostering adherence behavior in chronic disease management broadly.²⁹⁻³⁰ We will develop a bank of text messages tailored to intervention content and oriented towards behavioral activation to follow up with resources. Text messages will be sent to participants 3-5 times per week (4-5 times per week for intervention participants and 3-4 times a week for control participants) for 52 weeks. The intervention text messages include content about CareAvenue, whereas the control messages do not. Both intervention and control participants will receive a text message each week asking them to respond with how they rate their diabetes management. A feedback text response will be sent back to participants based on their diabetes management rating. IVR calls allow patients to receive information and respond using their mobile or landline telephone. Additionally, for the intervention participants we will develop IVR messages that inquire about follow-up with resources and ease of access, and automated messages back to the study team if the participant reports needing additional help in navigating resources. IVR calls will be placed on days and times that the intervention participant indicates are convenient, with automatic callbacks in the event that the call is not completed. Each call will take less than 5 minutes to complete, depending on patients' responses. In prior studies, patients have completed more than 80% of weekly IVR assessments over the course of a year.²⁵⁻²⁸ Both IVR and text messaging will be supported by the HIPAA-compliant platform within the University of Michigan Health System.

Pilot Amendments: Amendment 00086864/Amendment 00088719

We will first develop a prototype of CareAvenue refinements and pilot results with a group of 5 participants with type 1 or type 2 diabetes. Participants will be recruited from the UM Health Research Participant Registry and will have varying literacy levels. Participants will be recruited by phone. One-on-one interviews will be conducted with participants at the Ypsilanti District Library. Participants will be asked to complete 3 one-on-one interviews. The 3 interviews will test the CareAvenue prototype for the following:

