7 DATA COLLECTION AND MANAGEMENT PROCEDURES

7.1 Data collection

Participants will complete 3 data collection appointments. Each appointment will last approximately 90 minutes and will consist of a survey assessment, an HbA1C test, and two blood pressure readings. Participants enrolled prior to AME00101220 were enrolled in-person and completed surveys and assessments in-person; following AME00101220 all surveys and assessments for all participants are conducted virtually via phone. The baseline survey will be

given to participants prior to randomization. At the baseline appointment participants randomized to the intervention group will be asked to engage with the CareAvenue website on a tablet provided for use on-site or on own personal devices for virtual appointments. They will be asked to complete the website, which will take up to 20 minutes, and will also be provided a unique username and ID to login to the website on their own time.

Trained research staff will collect survey data via a computer-assisted interview through the use of Qualtrics software. We will assess HbA1c with an HbA1c machine. For in-person appointments research staff will be trained in best practices for HbA1c assessment by staff of the University of Michigan Department of Pathology. Once trained, research staff can train additional staff on use of the HbA1c machine. The HbA1C reading will be entered into Qualtrics. We will take the participant's blood pressure readings using an automatic blood pressure monitor. The blood pressure readings will also be entered into Qualtrics. Participants completing virtual appointments will obtain these measurements using at-home testing supplies provided by the study team.

All data will be downloaded from Qualtrics into a CSV file. This file will then be uploaded into SAS to create the study database.

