Intervention participants will be asked to give their provider their CareAvenue-generated action-plan to alert them of their needs and possibly receive additional support in accessing services. Although the intervention is targeted at the individual, physicians may change their behavior based on their interaction with treatment group patients and begin to better address unmet needs with control patients, thus raising the issue of contamination. That is, due to interactions with intervention patients, providers may alter “usual care.” This could diminish the effect size between intervention and control patients. One solution to this problem would be to conduct a cluster-randomized trial, which would obviate such contamination. We concluded, however, that because of the large number of unique providers seeing patients in the Diabetes Registry, the likelihood that a doctor will have patients in each arm is low. Further, some cross-over is inevitable because many patients in the Diabetes Registry see both a specialist and primary care provider, who may be randomized to different arms. Finally, a cluster randomized design would have required a large increase in sample size and cost. Although potential contamination lowers the treatment effect, we consider our design a strength of the study compared to a cluster randomized trial because baseline and follow-up assessments will allow us to quantify how much the control group also benefited from increased communication about low-cost treatment options with providers in the absence of the e-Health tool (comparing pre- and post- data among control patients within providers). This will demonstrate a generalized effect for the whole practice. We have increased the sample size by 3% to account for the potential that physicians’ behavior will spill over onto control patients. To account for a potential 12% loss to follow-up, we will recruit 600 participants. Based on our preliminary data from the pilot study and co-investigators’ prior studies with this population, we expect the following survey response rates: recruitment (72%), baseline (87%), follow-up 1 (94%), and follow-up 2 (80%).

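### The planned pre-post comparison in controls cannot measure provider spill-over or demonstrate a practice-wide effect, as section 10 says it will

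*Combined protocol and SAP*

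**What the plan says.** Section 10 (Statistical Considerations) discusses contamination: doctors who see intervention patients may change how they treat control patients. It gives reasons for not randomising by cluster, then calls individual randomisation a strength because the assessments will let the team "quantify how much the control group also benefited from increased communication about low-cost treatment options with providers in the absence of the e-Health tool". The method is given in brackets: "comparing pre- and post- data among control patients within providers". The conclusion follows: "This will demonstrate a generalized effect for the whole practice". Section III.A of the Data and Safety Monitoring Plan repeats the argument almost unchanged.

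Earlier in the same paragraph, section 10 says that "the likelihood that a doctor will have patients in each arm is low".

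Other sections that bear on the claim:

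- Section 6.1: "We will test our hypotheses using a two arm-randomized control trial". There is one control arm, and every control receives contact details for the health system's Guest Assistance Program, whose social workers help clients obtain resources.
- Section 6.3.2: texts are sent "3-4 times a week for control participants" for 52 weeks. Both arms rate their diabetes management weekly and receive a reply based on the rating.
- Section 6.4: surveys at baseline, 6 and 12 months cover cost-related non-adherence, financial burden and communication with professionals.
- Section 7.1: participants enrolled before an amendment started in person; "following AME00101220 all surveys and assessments for all participants are conducted virtually via phone".
- Section 8: no provider or practice term, no exposure variable and no spill-over analysis is listed.

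**The concern.** The paragraph names a quantity (benefit to controls from provider communication), a method (change over time in controls, within providers) and a conclusion (an effect across the practice). The method is an uncontrolled one-arm comparison, while the conclusion is causal and reaches beyond the trial's participants. Followed as written, the plan would attribute change in controls to one cause among several that act over the same months. What is at stake is a secondary statement about spill-over and one of the arguments for the design. The estimate of the intervention's effect is not at stake.

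**Working it through.** **1. The plan's figure for spill-over.** The only number tied to this argument is the sample-size allowance. Inputs, all from section 10: 510 participants with outcome data (taken as given here), 3% added for spill-over, 12% loss to follow-up, 600 recruited.

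- 510 × 1.03 = 525.3, rounded up to 526.
- 526 / (1 − 0.12) = 597.7, rounded up to 598. This agrees with 600.

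The required sample size varies as 1/(difference)², so a 3% increase offsets a dilution *d* where 1/(1 − *d*)² = 1.03:

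- *d* = 1 − 1/√1.03 = 0.0147, about 1.5%.
- 0.53 × (1 − 0.0147) = 0.522, a loss of about 0.008 HbA1c units.

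The sample size therefore makes room for only a slight spill-over. This is a planning allowance and not a forecast, but it sits oddly beside an effect said to reach the whole practice.

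**2. What control change contains.** Write the mean change in controls as

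C = S + G + T + Q + P + M

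| Term | Source of change | Where stated |
|---|---|---|
| S | Spill-over through providers | Section 10 |
| G | Assistance-program contact | Section 6.1 |
| T | Texts and weekly feedback | Section 6.3.2 |
| Q | Repeated questions on cost and communication | Section 6.4 |
| P | Time trends over a five-year study | Section 6.2 |
| M | Change from in-person to virtual assessment | Section 7.1 |

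The comparison yields C alone. For any value of S, the other five terms can sum to C − S and fit the same data. S is not estimable from it.

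Working within providers does not help. It removes stable differences between providers, but the competing terms are changes over time in the patient's contacts, the calendar or the measurement. The term M applies to participants whose baseline and follow-up fall on either side of the amendment; the documents do not say how many.

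**3. Exposure under the plan's own premise.** The sample size of 255 per arm implies 1:1 allocation. Assume independent allocation and a provider with *k* trial patients. The chance that a given control shares that provider with at least one intervention patient is 1 − 0.5^(*k* − 1):

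| Trial patients per provider (*k*) | Chance control is exposed |
|---|---|
| 1 | 0 |
| 2 | 0.50 |
| 3 | 0.75 |

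The plan's premise of low overlap holds only if most providers have a single trial patient. In that case most controls have no route to spill-over through that provider, and most of their change has other causes. If overlap is instead common, the premise used to defend individual randomisation fails. The premise and the practice-wide conclusion do not sit together.

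**4. Data and model.** I found no provision for recording which provider each participant sees, so the within-provider element has no stated data source. The covariates in section 8.2 are age, gender, race, income, insurance type, comorbidities and health literacy.

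**The case against.** The strongest reply is that this is a remark in the sample-size rationale with no analytic consequence. No endpoint, test, model or sample-size figure uses it. It is also not the only reason for individual randomisation: the same paragraph cites low overlap, patients who see both a specialist and a primary care provider, and the sample size and cost of a cluster trial. All of this stands, and it limits the severity. It does not make the sentence right, because the text promises a quantity by a named method and states what it will demonstrate.

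Several stronger readings are tempting and are not supported:

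- *No design of this kind could inform spill-over.* A comparison of controls whose provider does or does not also treat intervention patients, allowing for the provider's number of trial patients, could give partial information if providers were recorded. It is not planned. The criticism applies only to the planned pre-post comparison.
- *A null primary result would be explained away as spill-over.* Nothing in the documents says so. The text speaks of benefit from communication with providers, which has its own self-report measure.
- *The mode switch or the pilot gives a size for control drift.* The documents give neither the shift in HbA1c from home testing nor the share of participants affected. The pilot changes in Table 1 come from people who had used CareAvenue.
- *Regression to the mean from selection on high HbA1c drives control change.* HbA1c is remeasured at the study baseline, so this is a lesser point, and the conclusion does not need it.

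It can also be said that home HbA1c testing does not distort a survey answer about communication. That is fair, but section 7.1 moved the surveys to the telephone as well. The other competing causes remain in any case.

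**Conclusion.** Wrong as written, and of low severity. The planned pre-post comparison can describe change in controls, including change in their reported communication with providers. It cannot attribute that change to spill-over or extend it to a practice. No size can be given, because the planned data do not separate spill-over from the other causes. The randomised primary comparison is unaffected: time trends, repeated surveys and the change of mode bear on both arms, and the documents already acknowledge that spill-over would dilute the difference.

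The conclusion rests on the control-arm contacts in sections 6.1 and 6.3.2 and on the lack of a comparator free of spill-over. It needs no assumed magnitude. The exposure figures assume independent 1:1 allocation and serve only to show the conflict within the paragraph.

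**What to change.** In section 10 and in section III.A of the Data and Safety Monitoring Plan:

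1. Delete the sentence "This will demonstrate a generalized effect for the whole practice".
2. Replace *quantify* with *describe*.
3. Add: 'Change in the control arm will be reported descriptively and will not be attributed to spill-over through providers.'
4. Stop citing this comparison as a strength over a cluster trial. The reasons of cost, sample size and low provider overlap remain.

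The change is to wording only. It gives up one claimed advantage of the design and requires no new data, analysis or participants.

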11 REGULATORY REQUIREMENTS

11.1 Informed Consent

Participants who meet inclusion criteria will be consented over the phone or in-person prior to their baseline assessments (survey, HbA1C, and blood pressure testing) by trained study staff. All consenting will take place in private rooms (University of Michigan offices or research exam rooms located at Domino's Farms or other University of Michigan location). All potential participants will be given a copy of the consent form to read before consenting or research staff will read the entire consent form aloud (if requested by the participant). Potential participants will be allowed to ask any questions they have and the voluntary nature of the study will be emphasized. The study team will always use the most current IRB-stamped and approved consent form.

11.2 Participant Confidentiality

The researchers will take steps to minimize the risk of breach of patient confidentiality through data safety procedures as outlined in this protocol, section 7.3 Data Safety.

In order to efficiently and cost-effectively enroll large enough pool of eligible participants to show meaningful difference in study outcomes, we will obtain participants' diabetes diagnosis and most recent HbA1C levels from the DRR and DataDirect. This information will only be used for recruitment purposes and will not be stored for analysis.

This study evaluates change in outcomes over time, therefore, participants contact information must be retained in order to reach them throughout the study. This information must be linked to the data in order to evaluate outcomes at the 3 different data collection points.

A certificate of confidentiality is included as it is an NIH funded study. All NIH studies are automatically issued a Certificate of Confidentiality as part of the terms of the award.

11.3 Reporting Adverse Events, Other Reportable Events and Occurrences, and Unanticipated Problems

See Appendix 5 for the studies Data Safety Monitoring plan which outlines reporting and oversight for all AEs, ORIOs, and UaPs. This project will be overseen by a Data Safety Monitoring Board. The DSMB Charter is attached in Appendix 3 of the DSMP.

Appendix 1: Study Timeline

	Pre-Award	1	2	3	4	5	Year
Finalize protocol	●						
Clinicaltrials.gov registration	●						
Institutional Review Board Approval	●						
Agreement set up with Diabetes Registry	●						
Refine and finalize intervention		●					
Recruit participants and implement the intervention		●	●	●			
Enrollment of first participant		●					
25% of project recruitment			●				
50% of project recruitment			●	●			
75% of project recruitment				●			
100% of project recruitment				●			
6-month follow-up			●	●	●	●	
12-month follow-up				●	●	●	
Completion of data collection					●	●	
Data cleaning and entry			●	●	●	●	
Interim analysis				●	●		
Primary and secondary data analyses					●	●	
Prep for dissemination					●	●	
Manuscript preparation; grant submissions							●
Reporting results in clinicaltrials.gov							●
Publication of primary trial results							●

Appendix 2: Participation Flowchart

Appendix 3: CareAvenue Intervention Website Overview Diagram

Appendix 4: Data Safety Monitoring Plan

Data and Safety Monitoring Plan

NIH Study Number: 1 R01 DK116715-01A1

Title: Improving diabetes outcomes and health disparities through a patient activation intervention addressing unmet resource needs

Principal Investigator: [name], MPH

I. Overview

A. Study Purpose

The purpose of this study is to determine the extent to which activating diabetes patients to address health-related financial burdens that impact treatment adherence and unmet social risk factors improves disease control, and the mechanisms through which primary and secondary outcomes are achieved. The goal of this study is to evaluate CareAvenue on health outcomes- an automated, e-health screening, feedback and skills training intervention that addresses health-related financial burden and unmet SDHs.

B. Adherence Statement

The Data and Safety Monitoring Plan (DSMP) outlined below for (1 R01 DK116715-01A1) will adhere to the protocol approved by the University of Michigan Institutional Review Board (IRBMED), National Institute of Diabetes and Digestive and Kidney Disease (NIDDK), and the study Data Safety Monitoring Board (DSMB).

C. Data and Safety Monitoring Board (DSMB)

The purpose of the study DSMB is to monitor the safety and conduct of the study. The responsibilities of the DSMB are outlined in the charter.

II. Adverse Events, Other Reportable Incidents and Occurrences, and Unanticipated Problems

A. Assessment of Participant Risks

Potential risks for this study include:

- A common side effect of the finger stick blood draw is localized discomfort or bruising
- In rare cases, infection may occur as a result of the capillary blood collection
- In rare cases, fainting may occur as a result of the capillary blood collection

Discomfort, bruising, fainting, infection, or any other unexpected adverse reactions to the capillary blood collection will be documented. All identified risks are addressed in the study protocol and have been outlined in the study consent form.

All research staff will undergo training in line with university and federal guidelines. Staff of the University of Michigan Department of Pathology will thoroughly train research staff on taking HbA1c assessment using established protocols that emphasize sanitation, cleaning the site of the prick with alcohol before and after, and properly disposing of gloves and fingersticks after each assessment. Once trained, research staff can train additional staff on use of the HbA1c machine. All research staff will undergo Biosafety Training for Laboratory Personnel offered by the University of Michigan Institutional Biosafety Committee. First aid will be available onsite at the location of testing. Study HbA1C testing protocols can be found in Appendix 1.

i. Adverse Events

Adverse Events (AEs) are events that involve physiological, social, economic, or psychological harm to subjects. They may include symptoms, abnormal test results, a response to the study procedures, or any combination of these. Adverse events may also indicate risks of harm to other

subjects or others who are not study subjects but may be affected directly or indirectly. AEs include harmful effects that are both expected and unexpected.

The study will rely on self-reporting by study participants of adverse events. All participants will be provided with contact information for the project manager and study PI. Both in the study consent form and through verbal instructions from data collection staff, participants will be instructed to contact the project manager and PI if they experience any of the expected potential adverse events or experience any other events, symptoms, or occurrences that are unusual for them to experience whether they believe they are related to the study or not. Additionally, the study team will formally assess for Adverse Events/Serious Adverse Events at the Follow-up 1 (6 months-post baseline) and Follow-up 2 (12-months post baseline) data collection time points. The study team will utilize case report forms to collect this information from participants. Specific safety data the study team will assess includes:

- Discomfort, bruising, infection, fainting or unexpected adverse reactions to the capillary blood collection for the HbA1c measurement
- Negative outcomes related to use of the CareAvenue website (intervention group), Guest Assistance Program services (control group), receiving IVR calls (intervention group), or receiving text messages (intervention and control groups). This includes participant concerns related to privacy and safety of their information.
- Events resulting in inpatient hospitalization, prolongation of existing hospitalization, or emergency department visits
- Death (reported to the study team by an individual acquainted with the participant)
- Other non-specified events the participant shares

In addition to self-reporting, all data collectors will be instructed to report any indicators of adverse events to the project manager as soon as possible and not more than by the end of the business day. Indicators of adverse events may be observations of study subjects during data collection or reports made by study subjects directly to data collectors during routine study contact. Once the event has been reported to the project Manager, the project Manager will inform the PI. The PI will review the event and make a determination on the expectedness and relatedness of the event to the study using the University of Michigan Medical School Office of Research guidelines (see Appendix 2). This will occur within 24 hours of the initial report of the adverse event.

ii. Other Reportable Incidents and Occurrences

Other Reportable Incidents and Occurrences (ORIOs) are events in which no one suffered actual harm but indicate that there is a potential for future adverse events to occur. This includes events that may increase risk, alter the risk-benefit assessment, affect a participant's willingness to participate in the study or any departure from the human subject protection regulations and policies set forth by the IRB, NIDDK, or in this DSMP.

iii. Unanticipated Problems

Unanticipated Problems (UaPs) are events that are unexpected, related or possibly related to the study, and suggests that participation in the study places the participant or others at a greater risk of harm than was previously thought. Unanticipated problems do not include events in which harm has already occurred (which would be classified as an adverse event) or events in which potential harm or risk to subjects occurs (which would be classified as an ORIO). UaPs may happen to participants or non-participants who are affected by a person taking part in the study.

B. AE reporting

1. All adverse events whether expected/unexpected or related/unrelated that are reported to the study team including: research associates; data collectors; study staff; and investigators will be documented.
2. An adverse event report will be generated for each event. The report will include: a description of the event; when the event occurred; how it was reported; any documentation that corroborates the event; and the likely relatedness of the event to the subjects' involvement in the study.
3. Adverse event reports will be sent to the study DSMB and IRBMed based on the study reporting timeline. Any actions taken by IRBMed will be reported to the NIDDK program officer. A summary of adverse events will be presented to the NIDDK program officer during annual reporting.
4. This study will use the University of Michigan Medical School Office of Research Adverse Event Reporting Timeline (see Appendix 2).
5. Any action resulting in a temporary or permanent suspension of this study, such as actions by IRBMed, the study DSMB, or investigators, will be immediately reported to the appropriate NIDDK program official.

C. ORIO reporting

1. All other reportable incidents and occurrences that are reported to the study team including: research associates; data collectors; study staff; and investigators will be documented.
2. The PI will determine if the event should be reported to the IRB immediately or at the scheduled continuing review (SCR) using the University of Michigan Medical School Office of Research guidelines for ORIOs (see Appendix 2).
 - a. If the ORIO requires reporting to the IRB within 7 days, the event will also be reported to the DSMB.
 - b. If the ORIO is reported to the IRB at the annual SCR, the event will be reported to the DSMB at their meeting prior to the CSR.
3. Any action resulting in a temporary or permanent suspension of this study, such as actions by IRBMed, the study DSMB, or investigators, will be immediately reported to the appropriate NIDDK program official.

D. UaP reporting

1. All unanticipated problems whether expected/unexpected that are reported to the study team including: research associates; data collectors; study staff; and investigators will be documented.
2. The PI will determine when the event should be reported to the IRB using the University of Michigan Medical School Office of Research guidelines for reporting UaPs:
 - a. Serious UaPs will be reported within 7 calendar days.
 - b. Non-serious UaPs will be reported within 14 calendar days.
3. All serious and non-serious UaPs will be reported to the DSMB within one week of reporting to the IRB.
4. Any action resulting in a temporary or permanent suspension of this study, such as actions by IRBMed, the study DSMB, or investigators, will be immediately reported to the appropriate NIDDK program official.

III. Safety Review Plan and Monitoring

Oversight of subject safety includes review of adverse events as well as study progress, data integrity and study outcomes.

A. Justification of sample size

We propose to enroll 600 subjects in this study. The hypothesis to be tested is that the intervention will lead to uptake of low-cost resources for health and unmet basic needs and reductions in CRN, thus leading to medication/regimen adherence and intensification. We expect the beneficial impacts from improved access to treatment recommendations and unmet basic needs can lead to improved HbA1c

management and control. A 0.5 or greater reduction in HbA1c, after adjusting for confounding covariates, is considered a clinically meaningful change in stabilizing or improving HbA1c control.¹ We designed the study to have 80% power at an alpha level of 0.05 to detect a change difference of 0.53 unit change in hemoglobin HbA1c between study arms, and a standard deviation of 1.46 based on early data collected in the study.² We will need a total of 510 subjects (255 per arm) with outcome data to show a 0.53 unit difference in HbA1c. With this sample size, we will also have sufficient power to detect differences in our other self-reported secondary outcomes.

Intervention subjects will be asked to give their provider their CareAvenue-generated action-plan to alert them of their needs and possibly receive additional support in accessing services. Although the intervention is targeted at the individual, physicians may change their behavior based on their interaction with treatment group subjects and begin to better address unmet needs with control patients, thus raising the issue of contamination. That is, due to interactions with intervention subjects, providers may alter "usual care." This could diminish the effect size between treatment groups. One solution to this problem would be to conduct a cluster-randomized trial, which would obviate such contamination. We concluded, however, that because of the large number of unique providers seeing patients in the Diabetes Registry, the likelihood that a doctor will have patients in each treatment arm is low. Further, some cross-over is inevitable because many patients in the Diabetes Registry see both a specialist and primary care provider, who may be randomized to different arms. Finally, a cluster randomized design would have required a large increase in sample size and cost. Although potential contamination lowers the treatment effect, we consider our design a strength of the study compared to a cluster randomized trial because baseline and follow-up assessments will allow us to quantify how much the control group also benefited from increased communication about low-cost treatment options with providers in the absence of the e-Health tool (comparing pre- and post- data among control patients within providers). This will demonstrate a generalized effect for the whole practice. We have increased the sample size by 3% to account for the potential that physicians' behavior will spill over onto control subjects. To account for a potential 12% loss to follow-up, we will recruit 600 subjects.

B. Safety and study progress reviews

Adverse events, ORIOs, and UaPs will be reviewed by the study PI as soon as they are reported. The DSMB will review all reported AEs, ORIOs, and UaPs annually at regularly scheduled meetings. Ad hoc meetings will be held to review serious adverse events, ORIOs, and UaPs. All AEs, ORIOs, and UaPs will be reported to and reviewed by the IRB based on the timeline in Appendix 2.

Adherence to recruitment and retention protocols will be reviewed by the PI on a regular basis through reports made by the project manager. Additionally, the DSMB will review adherence on an annual basis.

The annual report provided to NIDDK will include the following information:

- A summary of AEs, SAEs, ORIOs, and UaPs
- A comparison of AEs rates with those anticipated at the study outset
- Statement regarding any loss of confidentiality that occurred, if applicable, and remedial steps taken
- Any protocol deviations and remedial steps taken
- Any communications with the IRB
- Recruitment and retention over the reporting period including the reason for subject drop out
- Study progress toward stated aims
- A comparison of study progress to the timeline set at the outset of the study

C. DSMB guidelines for recommending action

The DSMB will monitor the safety and conduct of the study. The board will make recommendations to the study team which may include study protocol modification, study suspension, or study termination. The

recommendations will be made at the DSMB's discretion and in accordance with the following specific guidelines:

- If study recruitment is more than 50% behind the recruitment timeline
- If participants report repeated AE/SAE directly related to the study intervention or their study involvement
- If there are consistent breaches of patient confidentiality either at the data collection site or through storage of data
- The DSMB will request unmasking of closed session reports at its discretion and if analyses indicate:

Half of participants experience a significant increase in HbA1c levels through the course of the study as measured by the HbA1c collected at follow-up data collection time points

IV. Informed Consent

Informed consent will be obtained from each subject at entry into the study. Informed consent will be treated as an ongoing process. The process will begin with recruitment and continue throughout the subjects' involvement in the study. Subjects will be provided with the consent form prior to baseline data collection. Subjects will be given time to thoroughly read the consent form and ask any questions prior to signing the form. Data collectors will offer to read the entire consent form aloud to the subject. At subsequent data collection points, data collectors will reiterate that participation is voluntary and that subjects may withdraw at any point in time from the study.

V. Data Quality and Management

A. Data collection review

All screening and survey data will be downloaded on a weekly basis for auditing and to identify and address any data discrepancies. All data will be collected and entered by research staff. The data manager will be responsible for downloading and auditing all data. In addition to review of data collection by the data manager, the DSMB will review the data on an annual basis and ensure that protocols are being followed in data collection and the quality of the data is not compromised. Internal interim monitoring will occur on a regular and continuous basis in the form of data collection auditing and safety data monitoring throughout the study. As noted in the charter, the unmasked biostatistician will prepare reports on a semi-annual basis.

B. Measures to insure data integrity and protection of databases.

All data will be collected through Qualtrics which uses Transport Layer Security to encrypt information. Data will be downloaded and audited for data quality on a weekly basis by the Data Manager. The Data Manager will store all downloaded data in a secure, password protected, encrypted University of Michigan drive. Back up databases will be stored before a new download is initiated. No databases will ever be overwritten. Access to the drive storing the databases will be restricted to the PI, Data Manager, project manager, and study biostatistician.

VI. Confidentiality

In order to maintain subject confidentiality, all study staff will be trained in Good Clinical Practice and Responsible Conduct of Research. The Data Manager will audit data collection processes on a weekly basis in order to ensure study procedures related to data safety are being followed. Any issues will be reported to the project manager and PI. Weekly meetings will be held between the project manager and research staff and data collectors to provide an opportunity for discussing general interviewing issues and issues of confidentiality. The project manager will report directly to the PI on a weekly basis or per the timeline listed above in the case of adverse events.

All recruitment and data collection activities will take place in private rooms to help protect subjects'

privacy.

All data collected will be coded so that no direct subject identifiers are linked with the data. Access to the code that links data with subject identifiers will be held only by the Data Manager and project manager. All other research staff, including the data collection staff, and the investigators will only have access to specific and select information on an 'as needed' basis in order to conduct recruitment, data collection, or the intervention. The coded database will be password protected and stored on a secured, encrypted University of Michigan drive.

When data must be shared for study purposes (e.g. potential Diabetes Registry subject lists, reports to the DSMB), it will be shared through the University of Michigan School of Public Health secure, HIPAA-compliant fax line or stored virtually via a secure, HIPAA-compliant web application hosted by the University of Michigan, DropBox at U-M, or through MiShare, a secure virtual file transfer system hosted by Michigan Medicine Health Information Technology & Services (HITS).

Participant data for IVR calls will be maintained by a HIPAA-compliant platform within the University of Michigan Health System. All participant data collected and transmitted through the intervention website will be sent encrypted via TLS/SSL secure transfer.

SMS participant data will be stored on HIPAA-compliant University of Michigan servers. In order to send and receive SMS messages, the SMS platform will transmit and receive messages through Twilio. Messages will be automatically redacted on Twilio's servers, to ensure that participants' messages and identifiable data such as phone numbers are not stored in Twilio's logs.

The CareAvenue website will not have access to any participant identifiers. The website will only collect responses to content questions and progress of website completion. Progress of website completion will be securely transmitted through an application programming interface hosted on a HIPAA-compliant server within University of Michigan Health System and will be encrypted using TSL or SSL encryption.

